6.5.3 Telephone / E-mail Follow up (Visit 3)

Participants will be contacted by telephone or e-mail approximately four weeks (visit 3) post-randomization to review medication compliance and pill diary, adverse events and any changes in fish consumption. Participants with <80% apparent adherence to study medication will be counseled to increase compliance so that their adherence at 8 weeks will be $\geq 80\%$.

6.5.4 Completion Visit (Visit 4)

Participants will come to the CTCRC after a 12 hour fast. Participants will meet with a study coordinator who will assess changes to the medical history and medication use. They will also be asked to record all food and beverages consumed on dietary records on 3 days prior to the visit. Any adverse events will be recorded, pill diary reviewed, and study medications will be counted (pill count) Weight and height will be recorded and BMI calculated. ECG will be performed. Blood will be drawn for post-drug screening of liver functions and chemistries as well as for all outcome-related measures (lipids, insulin/glucose, inflammatory markers). Urine for efficacy measures will also be collected. Urine pregnancy test will be performed in all females. Saliva and subgingival plaque samples will be taken to assess for any change in oral microbiome by the treatment. An adipose biopsy will be performed as per Section 6.4.

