In order to establish effects of treatments on adipose inflammatory parameters, we will obtain gluteal region subcutaneous adipose tissue biopsies under local anesthesia (2% Lidocaine). A detailed description of the adipose collection procedures is given in Section 6.4. Participants will then be randomized to drug or placebo group. Supplies of study drug will be provided to last 8 weeks (4 pills/day of either Lovaza or placebo).

Participants will be provided verbal and written instruction to take the study drugs as follows; 2 fish oil/placebo with food in the morning, 2 fish oil/placebo with food in the evening. A pill diary will be given to all subjects.

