7.1 Lovaza-study related safety measures

The most common reported side effects with Lovaza are burping, infection, flu symptoms, upset stomach, change in sense of taste, back pain and skin rash. We will monitor for development of these side effects at follow-up Visit 3 and Visit 4 and volunteers will be encouraged to contact the study coordinator or PI if these side effects

occur or become bothersome. There is a risk of an increase in alanine aminotransferase (ALT) and/or low-density lipoprotein cholesterol (LDL-C) levels; therefore we will be monitoring participants' ALT and LDC-C levels at Visit 2 (baseline) and at study completion. There is a possible association between Lovaza and more frequent recurrences of symptomatic atrial fibrillation or flutter in patients with paroxysmal or persistent atrial fibrillation. Thus there will be an ECG at visit 1 and subjects with arrhythmias will be excluded. ECG will also be done at end of study to assess of any potential induction of arrhythmias by use of study drug. Subjects will be discontinued as described above in Section 6.6.

If any of the above responses occur, the specific AE will be assessed with the circumstance of the occurrence, and discussed with the DSMB, NIH, and University of Pennsylvania IRB in order to outline a response / plan that accounts for this occurrence. Once the AE has been assessed, dosing will resume according to protocol.

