APPENDIX B

Pre-screening E-mail Questionnaire

Hello,

Thank you for your interest in the FAIR study. We are looking for healthy volunteers to participate in a study to better understand the anti-inflammatory benefits of prescription fish oil supplements that are currently used to help people with cholesterol problems. If you qualify, your participation would last about 3 months during which time there are 3 visits to the Clinical and Translational Research Center (CTRC) at the Hospital of the University of Pennsylvania.

Visit 1 is an outpatient screening visit which is about 2 hours long.

Visit 2 is a baseline visit which lasts about 2 hours

Visit 3 is a follow-up visit conducted via e-mail and/or telephone (you do not need to come to the CTRC)

Visit 4 is a completion visit which lasts about 2 hours

Visits may include blood sampling, urine collection, blood pressure measurements, fat-tissue sampling, fasting and brief physical exams.

Volunteers who complete all study visits will be compensated \$180 for time and travel.

If you would like more information and to see if you may qualify, please answer the questions below and reply back to me. A member of our study team will be in touch with you as soon as possible.

- 1) Name:
- 2) Gender:
- 3) Phone Number:
- 4) Email:
- 5) Age:
- 6) How did you hear about the study?
- 7) Do you have a history of diabetes (type 1 or type 2) or are you on any medications to lower your blood sugar?

- 8) Do you have any history of abnormal heart rhythm or other heart problems?
 1. If yes, what are they?
- 9) Do you have any other medical conditions for which you are under a doctor's care?
 1. If yes, what are they?
- 10) What is your height?
- 11) What is your weight?
- 12) How often do you eat-- as a main course-- tuna or other non-fried fish? (One serving size is 3 oz = in size to a deck of cards. Note: One serving of non-fried fish could include: 1, 3 oz. filet of salmon OR 6 pieces of sushi OR 8 sushi rolls OR ~4 tuna fish (salad) sandwiches, etc.)
 - A) Once or less per month
 - B) 2-3 times per month
 - C) Once per week
 - D) Twice per week
 - E) More than twice per week
- 13) Have you taken any fish oil supplements in the past 3 months?
- 14) What medicines, including supplements (like Omega-3 or fish oil) and vitamins, do you currently take and how often do you take them?
 - 1.
 - 2.
 - 3.
 - 4.
 - 5.
- 15) Do you have any history of gall bladder disease?
- 16) Do you have any allergies to fish?

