3.1 General Risk Considerations

The risks associated with blood draws include mild discomfort, occasional bruising and a small risk (< 1%) of infection. The total amount of blood that will be drawn at the screening visit is approximately 20ml. The total amount of blood that will be drawn at the randomization visit (Visit 2) is 50ml and again 50 mL at the completion visit (Visit 4). Overall, this is significantly less than 1 pint of blood which is well within the recommended allowance over a span of 2 months. The risks associated with subcutaneous fat aspirations include bleeding, bruising, infection and pain. These will be minimized by using a trained physician to perform the procedures, administration of anesthesia to reduce pain, and careful monitoring of the aspirated sites by nursing.

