4.0 Patient Safety Education

During the initial enrollment phase, all prospective participants will have the entire protocol described to them in detail and will be informed of all risks and potential benefits of participation. This explanation is a part of the informed consent process. Once enrolled, subjects will be educated about the risks of LOVAZA responses, , adipose biopsies and other study procedures. All patients will be given practical advice on identifying and reporting any adverse events including infection, inflammation or bleeding at biopsy sites. Patients will be asked to notify the research study investigator, coordinator or CTSC nursing staff in if they are experience symptoms related to the above-mentioned risks or any other adverse events.

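### No contact is scheduled after the Visit 4 adipose biopsy, so its delayed complications rest on participants' own reports, and the Safety Plan's biopsy-site check belongs to a visit that is not in the schedule

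*Combined protocol and SAP*

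**What the plan says.** **Visit 2 (Section 6.5.2).** The first biopsy is taken, after which "Participants will then be randomized to drug or placebo group". Drug is dispensed at the same visit: "Supplies of study drug will be provided to last 8 weeks".

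**Visit 3 (Section 6.5.3).** A telephone or e-mail contact at about week 4 reviews adverse events.

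**Visit 4 (Section 6.5.4; week 7 to 9 in Appendix A).** "Any adverse events will be recorded, pill diary reviewed, and study medications will be counted (pill count"). The same paragraph closes with the second biopsy: "An adipose biopsy will be performed as per Section 6.4". Appendix A has no later column, and Appendix B tells volunteers that "Visit 4 is a completion visit which lasts about 2 hours".

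**How events are collected (Section 6.3.1).** The standard questions are asked at check-ins and look back to the previous visit. Spontaneous reports are also recorded. Collection starts at the first dose; no end is stated.

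**Biopsy risk (Appendix D).** Section 3.1: "The risks associated with subcutaneous fat aspirations include bleeding, bruising, infection and pain". It adds that nursing will watch the sites, without saying for how long. Section 4.0: "All patients will be given practical advice on identifying and reporting any adverse events including infection, inflammation or bleeding at biopsy sites". Section 3.5 names a check for biopsy-site inflammation, infection or haematoma, but places it at the end of an inpatient endotoxemia visit, Visit 5.

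**The concern.** The standard questions look backwards, so an event is solicited only if a later check-in exists. The first biopsy has one at week 4. The second has none, and a site infection or late bruise can hardly be expected to show itself within a visit of about two hours, wherever in that visit the biopsy falls.

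What is at stake is safety ascertainment. The Safety Plan names the biopsy risks. It lets visits and enrolment be halted for clinically significant unexpected events related to study procedures (Appendix D 6.2), and it promises the DSMB reports with a statistical analysis of adverse events (Appendix D overview). Both depend on biopsy complications being captured, and for the second biopsy that capture is passive. It is also the only biopsy taken after about 8 weeks of drug or placebo.

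**Working it through.** **1. The two biopsies side by side**

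| | Visit 2 biopsy | Visit 4 biopsy |
|---|---|---|
| Timing | Week 0, before randomisation | Week 7 to 9, at or near the end of dosing |
| Later scheduled contact with adverse-event review | Visit 3 (about week 4), then Visit 4 | None |
| Planned number | About 52 (Section 5.1) | About 44 completers (Sections 4.0 and 5.1) |

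The supply lasts 8 weeks, so a Visit 4 at week 9 may fall up to 9 − 8 = 1 week after the last dose. Hence at or near the end of dosing, rather than on drug.

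**2. The plan's own sample size**

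The documents give no figure for biopsy complications. The design figure that sets the number of biopsies is 22 completers per arm (Section 9.1). At 0.9 SD, 80% power and alpha 0.05 (taken as two-sided; the plan does not say), a t-test needs 20.4 per group. Dividing by the Wilcoxon efficiency, 3/π = 0.955, gives 21.3, rounded up to 22. Simulated Wilcoxon power at 22 per group, with normal data, is 0.82. The figure reproduces. Completers: 2 × 22 = 44. Randomised, as the plan states: 2 × 26 = 52.

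**3. Share of biopsies with no scheduled contact afterwards**

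- 44 / (52 + 44) = 44 / 96 = 45.8%.
- If all 52 randomised participants attended Visit 4: 52 / 104 = 50%.

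**4. Number of missed events**

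Missed events = 44 × p × (1 − r), where p is the delayed-complication rate and r is the share that participants report unprompted. The documents give neither. Taking p as 1%, 5% or 10% (assumptions), 44p is 0.44, 2.2 or 4.4 complications in all. The number missed lies anywhere from zero (r = 1) to that total (r = 0), so no figure for missed events can be given.

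**5. What a comparison between arms could show**

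Fisher's exact test, two-sided 0.05, 22 per arm, full capture, assumed rates:

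| True rates | Power |
|---|---|
| 5% vs 15% | 9% |
| 5% vs 20% | 20% |
| 5% vs 30% | 51% |
| 5% vs 40% | 77% |

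With no events in one arm, 4 in the other gives p = 0.108 and 5 gives p = 0.048. No events among 22 leaves a one-sided 95% upper bound of 1 − 0.05^(1/22) = 12.7%. If only half of the events were captured in each arm, power for 5% vs 30% would fall from 51% to 14%.

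**6. Safety Plan against schedule**

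Appendix D 3.5 attaches its biopsy-site check to Visit 5. Appendix A and Appendix B list Visits 1 to 4 only. As written, that check cannot take place in this trial.

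**The case against.** The best reply is that other routes exist. Nursing watches the sites, participants are told how to recognise and report biopsy-site problems, and spontaneous reports are recorded. Section 14.1 covers events discovered by any other means, and Appendix D 5.4 asks participants to report serious events promptly. No end to collection is stated, so a late report would not be refused. The consent form, which is not in the public text, may add aftercare instructions. All of this stands. It means that late events are collected passively; it does not mean that they go uncollected.

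For the same reason, some stronger readings that a reader might infer are not supported:

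- *The biopsy is the last act of the visit.* It is listed last, but Section 6.5.4 gives no order in time. The point does not need one.
- *No communication at all follows Visit 4.* Appendix D 3.5 requires participants to be notified of significant abnormalities found at Visit 4. That is a conditional notice, not an enquiry about events.
- *Complications of the first biopsy cannot differ by arm.* Biopsy, randomisation and dispensing share one visit, so a delayed complication can develop after dosing starts. It is then collectable, and Visit 3 asks about events. Pre-dose events are collected only if they worsen (Section 13.5).
- *Biopsy bleeding cannot be compared between arms.* Reported events can be tabulated by arm. The table would be incomplete, and 22 per arm is too few for a firm comparison even with full capture.
- *The plan itself treats biopsy bleeding as a reason to discontinue.* Section 6.6 illustrates significant bleeding with gastrointestinal, cerebral and major ENT bleeds, not a bruise at a small incision.

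Section 7.1 says of common Lovaza side effects: "We will monitor for development of these side effects at follow-up Visit 3 and Visit 4". That covers drug symptoms up to Visit 4 and does not reach beyond the second biopsy.

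**Conclusion.** The point holds as a gap in safety ascertainment. No scheduled contact follows the Visit 4 biopsy, so delayed complications of the only biopsy taken after about 8 weeks of assigned treatment depend on participants' own reports or on site monitoring of unstated duration. About 46% of planned biopsies are affected, taking the plan's 52 randomised and 44 completing. The number of events lost is unknown, because neither a complication rate nor a reporting rate is given.

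Separately, and without any assumption, the biopsy-site check in Appendix D 3.5 conflicts with the visit schedule in Appendix A.

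Biopsy-site bleeding by arm is not a study objective and could not be tested usefully at this size. The case rests on participant protection and complete reporting. The primary endpoint, plasma CX3CL1, is unaffected.

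**What to change.** - Add one telephone or e-mail contact after Visit 4 to Section 6.5.4 and Appendix A, in the Visit 3 format, at an interval the sponsor sets. Ask the three standard questions of Section 6.3.1 plus the biopsy-site items already listed in Appendix D 4.0.
- State in Section 6.3.1 that adverse-event collection runs through that contact.
- Reconcile the Visit 5 text in Appendix D 3.5 with the four-visit schedule.
- Tabulate biopsy-site events by arm, descriptively, with no formal test.

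**Cost.** About 44 to 52 short contacts by existing coordinators, an amendment of the passages above, and slightly longer participation. No new visit, test or procedure is needed, and the sample size and primary analysis do not change.

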6.6 Study Discontinuation/Completion

A subject may be withdrawn from the study at any time at either the investigator's discretion or the subject's request. An effort must be made to document the reason(s) why a subject fails to return to the study clinic for necessary visits or is discontinued from the study. The primary reason for discontinuing participation in the study must be stated and may include, but is not limited to, one of the following:

- ◆ Development of any abnormality in blood counts, blood chemistries, or urinalysis because of which the investigator deems continued participation in the study to be ill-advised
- ◆ Use of unapproved concomitant medications

- ◆ Occurrence of intolerable AEs
- ◆ Development of LFT abnormalities (>1.5 ULN), unexplained muscle aches/myopathy, kidney dysfunction (Cr>ULN), or significant bleeding (e.g. GI bleed, cerebral hemorrhage, major ENT bleed).
- ◆ Withdrawal of consent by patient
- ◆ Noncompliance with protocol, e.g., the patient fails to appear at one or more visits
- ◆ Non adherence with study medications – defined as failure to take >80% of study medications (pill count and diaries)
- ◆ Development of an intercurrent illness, injury, or medical condition likely to interfere with patient safety, the overall assessment, or the required administration of study medication
- ◆ Development of any condition for which the investigator feels treatment withdrawal is justified
- ◆ Termination of the study by the sponsor (NIH)

The procedure to discontinue a subject from the study is as follows:

- ◆ record any AEs since previous visit
- ◆ record any medications
- ◆ record vital signs
- ◆ perform a physical examination (if discontinuation is due to an AE)
- ◆ collect blood for clinical laboratory analysis

Patients who discontinue from the study because of an AE(s) should be treated and followed according to established medical practice.

The study may also be discontinued at the discretion of the Principal Investigator, if any safety concerns are identified during the course of the study.

7.0 SAFETY MEASURES

A detailed description of all safety related issues including the risks of study, participant monitoring, adverse event data collection and reporting is provided in a formal Safety Plan (Appendix D) developed also for our Data Safety and Monitoring Board (DSMB). Therefore, in this section we briefly describe the safety measures that we will record and measure during the execution of the study. Additional safety-related details are provided in the Safety Plan.

7.1 Lovaza-study related safety measures

The most common reported side effects with Lovaza are burping, infection, flu symptoms, upset stomach, change in sense of taste, back pain and skin rash. We will monitor for development of these side effects at follow-up Visit 3 and Visit 4 and volunteers will be encouraged to contact the study coordinator or PI if these side effects

occur or become bothersome. There is a risk of an increase in alanine aminotransferase (ALT) and/or low-density lipoprotein cholesterol (LDL-C) levels; therefore we will be monitoring participants' ALT and LDC-C levels at Visit 2 (baseline) and at study completion. There is a possible association between Lovaza and more frequent recurrences of symptomatic atrial fibrillation or flutter in patients with paroxysmal or persistent atrial fibrillation. Thus there will be an ECG at visit 1 and subjects with arrhythmias will be excluded. ECG will also be done at end of study to assess of any potential induction of arrhythmias by use of study drug. Subjects will be discontinued as described above in Section 6.6.

If any of the above responses occur, the specific AE will be assessed with the circumstance of the occurrence, and discussed with the DSMB, NIH, and University of Pennsylvania IRB in order to outline a response / plan that accounts for this occurrence. Once the AE has been assessed, dosing will resume according to protocol.

8.0 DATA COLLECTION AND ANALYSIS

8.1 Source Documents & Case Report Forms

All primary primary records, such as original copies of signed consent forms, will be stored in a locked filing cabinet and will only be available to study investigators. The documents will be stored in files labeled only with a unique research identification number. Electronic copies of these documents will be created and stored within the REDCap database. These primary records will not be available to any future recipients of registry-repository data without separate IRB approval.

8.2 Computer Systems

All electronic data will be managed and stored using the research-focused electronic data capture system REDCap, under an agreement with the software's development consortium, led by Vanderbilt University. REDCap supports two secure, web-based applications designed exclusively to support data capture for research studies. REDCap is a PHP web application served by Apache Tomcat over a 128 bit SSL connection using a signed certificate. The application relies on a study-specific data dictionary defined in an iterative self-documenting process that will be conducted by all members of the research team. The data dictionary is the foundation for custom case report form design and validated coding of variables. Authentication of research staff will be performed via LDAP using CHOP's enterprise Active Directory service. The application generates a complete audit trail of user activity, provides reporting, and has an automated export mechanism to common statistical packages (SAS, SPSS, Stata, R/S-Plus).

The REDCap MySQL database is replicated in real time to a completely redundant instance of MySQL. The redundant instance is available for restoration of the primary database or for manual failover in the case of primary database failure. Time-stamped backup files are made from the replicated database daily by CHOP Research Information Systems using automated backup routines. Backup files are encrypted and transferred to a secure file server accessible only to designated personnel. A rolling seven-day window

of backup files is maintained in an immediately available online state, with a larger window maintained in a compressed file archive available at a reduced speed of access. Daily destructive database backup files are stored on the database server and are deleted only after successful backup of the entire database to file. In the event of data error, loss or corruption, Research personnel will work with CHOP Research Information Systems to determine the most appropriate recovery strategy.

Data and backups are stored in the CHOP Research Information Systems Storage Area Network (SAN). Access to the SAN directories where data are stored will be limited to Research Information Systems personnel, with authentication performed using CHOP's enterprise Active Directory service.

REDCap's extensive security features will be taken advantage of to limit PHI, and any links between this PHI and all other data, to only the study investigators listed on this IRB protocol. All other users, particularly future recipients of data output from the registry-repository, will only have access to data tagged with a unique research ID number.

9.0 STATISTICAL METHODS:

9.2 Statistical Analyses

Analysis will be performed by [name] with support from Penn Statistics faculty with expertise in human translational research ([name]). In the human trial, the primary endpoint will be compared between groups using two-sample Wilcoxon test, with graphical explorations and repeated measured ANOVA to explore the shape of changes over time. Correlations between circulating and adipose CX3CL1/CCL2 and monocyte/macrophage markers, systemic inflammatory markers and metabolic parameters will utilize Spearman's correlation. Differences among conditions in cell studies will be analyzed by ANOVA. All analysis will use STATA 11 (StataCorp).

All secondary/exploratory variables will be assessed as independent responses because they may reflect independent effects of the treatment. The multiple testing of non independent responses may result in type I error and false positive findings. Therefore, any statistically significant differences will be interpreted in terms of the overall significance level, considering multiple comparisons, and ultimately in the context of the clinical significance of the difference.

